As described above, the FACT-L v.4 contains four general and one lung cancer symptom-specific subscales. General subscales include: Physical Well-Being (PWB), Social/family Well-Being (SWB), Emotional Well-Being (EWB), and Functional Well-Being (FWB).(49) The Lung Cancer Subscale (LCS) assesses symptoms commonly reported by lung cancer patients (e.g., shortness of breath; loss of weight; tightness in chest). The Trial Outcome Index (TOI) is derived by adding scores on the PWB and FWB subscales to the LCS. Because they contain the most relevant questions about symptoms and physical functioning, the LCS and TOI were selected as the primary focus of this analysis. All FACT-L questions are rated on five-point Likert-type scales ranging from 0 (“not at all”) to 4 (“very much”). Therefore, because the seven-items PWB, FWB, and LCS subscales scores range from 0–28 for each subscale, TOI scores range from 0–84. Higher scores represent better QoL or fewer symptoms. The primary outcome is the change in the score on the TOI from baseline to 12 weeks. We estimated that with 120 patients (Figure 7), the study would have 80% power with a two-sided α of 0.05 to detect a significant between-group difference of 6 points in the change in the TOI score from baseline to 12 weeks, given a pooled standard deviation of 11.54 and change in the reference group score of 53.(50) After accounting for 30% attrition rate, the expected number of enrolled patients is 156 allocated 1:1 between LuCApp and usual care groups. This sample size will also allow the detection with 80% power with a two-sided α of 0.05 of 2-points difference in the LCS subscale, assuming

a pooled standard deviation of 4.15 and change in the reference group score of 19.3 (50) (Figure 8). The clinically meaningful changes on the TOI and LCS subscales of FACT-L were derived from Cella et al.(51)

The FACT-L questionnaire will be administered electronically (via LuCApp) or via paper in the control group at baseline, 12 weeks and 24 weeks, with an understanding that in the routine care setting, lung cancer therapies administration intervals vary between patients.

Figure 7 - Sample size estimation: 5 to 10 -point difference in change in TOI score at 12 weeks

[figure not shown]
[figure not shown]
[figure not shown]

Figure 8 - Sample size estimation: 1 to 5-point difference in change in LCS score at 12 weeks

Assuming a constant recruitment rate of 6 patients per week (2 patients per centre) the study is planned to recruit consecutively for 26 weeks (Figure 9).

Figure 9 - Planned recruitment process

Randomization

Randomization services will be provided by AdvicePharma via a computer system using randomly permuted blocks and stratified by trial centers and therapy (i.e.

chemotherapy, immunotherapy and biological therapy). Nurses or physicians involved in the study will take care of the enrollment phase. After signature of informed consent, a randomization code will be generated electronically and assigned to the patient. During the informed consent procedure, the team will go carefully through the different aspects of the study design and will present LuCApp as well as the usual care alternative. During this phase the patient will have an opportunity to discuss her level of experience with mobile technology.

The study is nonblinded, in fact it is not possible to blind the participants when this type of intervention and these outcomes are under investigation.

Participants will remain on study until discontinuation of cancer treatment, voluntary withdrawal, study termination or death.

Statistical methods

The baseline differences between the intervention and control groups will be assessed using the chi-square (χ^2) test for binary demographic data and the independent sample t-test for continuous variables. We will summarize graphically and numerically the distributions of symptoms, outcomes as well as covariates.

For the primary quality of life endpoint, two groups t-test will be used to compare changes from baseline in FACT-L in the experimental group and the control group 12 weeks after randomization. A multivariable linear regression model, with change score as the dependent variable, adjusted for covariates will be fitted. The proportion of patients in each arm who experienced improved, unchanged, or worsened scores from baseline will be compared using χ^2 or Fisher's exact test. This analysis will be run for both any change and clinically meaningful changes for specific subscales (51). The analyses will be repeated at 24 weeks after randomization.

For all other questionnaires, changes from baseline in the LuCApp group and the control group at 12 and 24 weeks after randomization will be computed using t-test comparison. The SCNS-SF34, usability and ZBI data results will be summarized graphically and numerically.

As a secondary analysis, adjusting for possible confounding factors of demographic variables and clustering in centers, the repeated measures multivariate analysis of covariance will be conducted to determine whether LuCApp affects HRQoL and symptoms as measured via EQ-5D-5L, FACT-L and HADS at different time points of

data collection. Additionally, mixed-effects models will be used to analyze the same subject-specific continuous outcomes with incorporation of terms for intervention, time, centers, and any identified covariates.

Analysis of missing data will first determine how common a problem this is and whether it can be assumed to be missing at random or not missing at random. Multiple sensitivity imputation analyses will be conducted, including last observation carried forward, minimum observation values carried forward, average observation values carried forward, and multiple imputation. EQ-5D value will be set to zero if death occurs before 6 months. Survival time will be calculated from the date of enrollment to the date of death or censoring those alive at the last follow-up with the use of the Kaplan–Meier method. A Cox proportional-hazards model will be fitted to assess the effect of LuCApp on survival, with adjustment for demographic characteristics and baseline performance status.

By combining EQ-5D derived utilities and survival quality-adjusted life years (QALY) for participants in both arms will be computed and compared using two group t-tests between LuCApp and standard care arm. A multivariable linear regression model with QALY as dependent variable will be used to adjust for other covariates. Resource consumption and related costs will be calculated and reported for each treatment group and compared by means of parametric and non-parametric tests (52).

Two-sided P values of less than .05 were considered to indicate statistical significance. All statistical analyses will be performed using STATA® 14.2, StataCorp, Texas.

Ethics & Informed Consent

All procedures involved in the study were consistent with generally accepted standards of ethical practice. The protocol is submitted for ethical clearance to the ethical committees at the three sites involved in the RCT (full list of participating centers is available as an attachment).

Patients will be informed about the study by their clinician during the enrollment visit. The oncologist will provide patients with a brief introduction of the trial content and will hand them over a leaflet where all relevant information is gathered. This will enable patients to make an informed decision about whether to take part in the study. The leaflet will better explain the App's "terms and conditions", will assure the confidentiality of the data collected and outline users' rights and responsibilities.

Safety, privacy and legality are guaranteed using a unique username with an associated password, firewalls, secured sites and the transfer of confidential information: whenever one of the previous is missing, the brochure will explain which procedures to follow during an emergency. Furthermore, a statement on how data will be stored and when they will be destroyed is included in the form.

To further support patients during the trial and increase security, an email “helpdesk” will be activated to help participants manage any kind of unexpected trouble.

Participant signature is required for informed consent. After signing it, patients will send the consent form both to the research team and to their clinician.

DISCUSSION

The electronic and mobile health revolution holds great potentials for improving symptom management strategies in chronic conditions. With spending review reforms under way, using web- and mobile-based technology to develop low cost and pragmatic patient-centered intervention is the key to lessening the health care cost and advancing the science of symptom management. In parallel with the development of new strategies and products, the evaluation of such interventions becomes important in order to bring to patients and to healthcare systems effective and cost-effective solutions. This clinical trial focuses on primary outcomes of health related quality of life and usability to test preliminarily the impact of LuCApp as a technology to improve self-reporting and self-management of symptoms in patients with lung cancer. The trial was designed with a pragmatic “attitude”, eligibility criteria were intentionally set wide to capture the lung cancer population seen in real practice. However, this trial is to be intended as a pilot one in order to understand the usability and feasibility of introducing a new mobile technology in the management of symptoms and side effects of patients undergoing pharmaceutical treatments for lung cancer in three centers in Northern Italy.

Dissemination and impact

The protocol will be registered on a public repository and possibly published on a peer reviewed journal. Once the study will be completed and the analyses will be performed, a report will be produced and shared with all participating centers for interpretation. A manuscript will be drafted by the team and submitted for publication at conferences and in scientific journals.

REFERENCES

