
• over 18 years of age individuals of both sexes;• diagnosed with small or non-small cell lung cancer;• patients eligible for chemotherapy, immunotherapy or biological therapy;• patients diagnosed with non-resectable tumor and eligible for neoadjuvant therapies;• life expectancy of six months or more;• a performance status between 0 (asymptomatic) and 2 (symptomatic, <50% in bed during the day) according to the Eastern Cooperative Oncology Group (ECOG) score;• patients fluently speaking Italian;• patients able to provide informed consent to participate in the study;• patients who own a smartphone that can access either the iOS or the Android platform.	
• individuals unable to provide written informed consent;• individuals unable to see the App and all other materials (i.e. are blind);• patients receiving or that plan to receive radiotherapy or surgical resection;• patients already included or about to join other clinical trials;• patients already using other smartphone applications to self-manage cancer symptoms.

Once eligibility has been established, patients will be asked to join the study by the medical oncologists after diagnosis and a face-to-face assessment at the participating centers. Patients will receive an invitation letter, the study leaflet and the informed consent form. This will not be a purely web-based trial, since face-to-face components will still be present: data will be collected through questionnaires via the app for the intervention patients, while standard-of-care patients will complete paper questionnaires during clinic visits, or at home (having received paper questionnaires during the previous visit) or via telephonic interviews with the research team. Outcomes will be self-assessed through Patient Reported Outcome Measures (PROMs) (for further information, please look at the “Outcomes” section) at different points in time. Patients assigned to the intervention arm will be trained to use LuCApp (study staff will provide them with a 15-minute presentation on how to use the App) and will be assisted during the whole study period by a “helpdesk”.

University and participating centers affiliations will be displayed on the invitation letter to obtain participants’ trust but no bias is expected to result from the display of such information.

Intervention (LuCApp)

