Figure 4 - An example of how trends for different symptoms and parameters are visualized in the app

- 6) “Info” – In this final section, in order to increase the overall awareness of the disease and its potential treatments, the most relevant educational material is collected. This section includes some general information on lung cancer, therapies, patients’ rights, up to a series of institutional useful links (such as nearest pharmacy, hospital contacts) that patients can browse if needed (Figure 5).

Figure 5 - An example of how information is visualized in the app

Continuity in the utilization of the application will be strongly recommended. Participants will be advised to access the App daily to receive their daily tip and enter their temperature information. Questionnaires and other clinical parameters will have to be entered according to the schedule, but additional information can be added at discretion and alerts will activate whenever necessary. Patients will be advised to enter their daily body temperature at similar times each day and to use the same scale to measure their weight. To facilitate a greater use of the application, LuCApp provides for several rounds of banner reminders (better detailed above) scheduled on days when the input of a specific information is due according to study protocol.

Patients in the standard of care will follow the routine procedures and will be assisted by a clinical team at their site. Such professionals will still provide frequent assistance related to the trial since they will administer questionnaires when due and will update the CRF for the standard of care patients. On the other hand, in order to deal with the intervention arm, healthcare professionals will be trained through dedicated sessions prior to the launch of the patient recruitment phase. Contact details of LuCApp developers and technicians will be provided for assistance. However, if the technology does not function properly and the clinician believes an action is urgently needed for a patient, the research team is advised that standard of care applies to the intervention arm, too. During weekends it is possible that clinicians will not be reachable or will not reply promptly to alerts. Also in this case patients are advised to use the standard of care approach (e.g. out-of-hours service doctor, emergency department). The clinical teams that will take care of the intervention patients will be different from the standard

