of care arm ones, to ensure that behaviors and results will not be influenced. The research teams are also advised not to share feedback or comments for the duration of the trial in order to reduce performance bias as much as possible. Clinicians will receive alerts on their dedicated LuCApp device and will be responsible for managing them in a timely way. A single alert will be generated for each patient and clinical parameter monitored (i.e. temperature, weight, side effects). Healthcare professionals will then be able to gain more information on the symptoms that triggered the alert and to monitor the longitudinal trend of side effects both on their device and on the LuCApp website from a PC or laptop. Professionals will be able to access all other patient information on the secure LuCApp website, only. In response to an alert triggered for a specific patient, clinicians will be requested to act within 24 hours and to document the type of intervention performed among a list of possible alternatives derived from the literature: referral to the ER/hospital, telephone counselling about symptom management, dose modification, supportive medication initiation/change, visit anticipation (13).

To guarantee a greater use of the application automated reminders will be sent to participants both via email and via push notification. Participants will be prompted, via an automated message to update their body temperature and their weight and to fill out the side effects questionnaires. Three rounds of alerts will be generated at 12, 6 and 9 p.m. on the dates when the input of the relative data is scheduled (daily for body temperature, weekly for weight and every three days for the side effects questionnaire, see above).

Both groups will have access to treatment as usual. However, additional training will be provided to intervention arm participants right after enrolment: LuCApp features will be better detailed and training sessions will be scheduled accordingly. Furthermore, during the trial, a support center (“helpdesk”) will be available to help participants with any technical issues that may occur.

Standard of care

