Usual care will consist of standard procedures currently available at participating centers for monitoring and documenting symptoms. These therapeutical procedures are based on the guidelines developed by the National Comprehensive Cancer Network (NCCN) and the Associazione Italiana di Oncologia Medica (AIOM) (20). Symptoms for control arm patients will be discussed and registered during scheduled clinical visits

with the oncologists. Standard-of-care patients will fill out their PROMs following the same schedule identified for LuCApp patients with paper questionnaires during clinic visits, or at home (having received paper questionnaires during the previous visit) or via telephonic interviews with the research team. Patients are usually allowed to contact their relative sites for concerning symptoms that occur between scheduled visits or advised to see the out-of-hour doctor or the emergency department if needed. This option is also recommended for the intervention arm during weekends.

Outcomes

As discussed above, the overarching research question of this study is to explore and pilot the impact of using LuCApp on relevant outcomes in patients with lung cancer. LuCApp has several functionalities and this pilot explores whether these functionalities impact on the patients' health-related quality of lives (HRQoL) and needs in cancer supportive care. It also aims to assess whether it improves the burden on caregivers and the satisfaction with the use of the app. Finally, the cost-effectiveness of LuCApp will be explored, based on the improvement in HRQoL and the resources being used to manage the disease throughout the study period.

A number of outcome measures have been identified to allow the assessment of the above trial objectives. LuCApp will be evaluated in terms of: (1) impact on HRQoL, (2) impact on cancer supportive care needs, (3) impact on the burden for caregivers, (4) resource use, (5) usability and satisfaction with LuCApp. The rationale for selecting these measures and their characteristics are summarized in the next sections.

(1) HRQoL

The impact on HRQoL of using LuCApp will be measured with existing valid and reliable patient-reported outcome measures (PROMs). Their selection was based on the availability of a validated Italian version, for self-report use, that can be administered both on paper and via smartphones or tablets, and commonly used in lung cancer patients.

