The Functional Assessment of Cancer Therapy-Lung (FACT-L) questionnaire is a disease-specific measure capturing multidimensional aspects of lung cancer patients' quality of lives (26). The symptoms covered are shortness of breath, weight loss, consciousness, cough, hair loss, appetite, tightness in chest, breathing. FACT-L is the result of the combination of FACT-G (general module and core instrument), which is a general quality of life questionnaire for use in a variety of chronic illness conditions, with a Lung Cancer subscale. It is validated in the Italian version. These questionnaires are extensively used in clinical research, health care delivery studies, symptom management studies, psychological intervention studies, and other treatment evaluations. Studied in various subgroups of lung cancer patients receiving different courses of treatment. The administration mode could be interviews (in-person or telephone), self-administration (in the clinic or by mail) or computer administered questionnaire. Available data suggest that while there are small differences in the way people respond based on mode of administration, these alternate formats are essentially

equivalent, particularly when reporting data at the group level (27). The questionnaire will be administered at baseline, at 12 weeks, and at the end of the study period.

c) Hospital Anxiety and Depression scale (HADS)

HADS is a self-assessment scale developed to detect states of depression, anxiety and emotional distress amongst patients treated for a variety of problems in the setting of out-patient clinics (28). It is composed of two 7-item scales for depression and anxiety respectively. All symptoms relating to physical disorders (e.g. dizziness, headaches) were excluded to avoid interference with other diagnoses (29). HADS was identified as one of the most commonly used PROMs in advanced-staged lung cancer clinical trials of pharmaceutical agents (30), and has been used to measure HRQoL in NSCLC patients (31).

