The ZBI was selected on the basis that it has been used in cancer patients (40) and is one of the most widely referenced scales in studies measuring caregiver burden (41). The ZBI was developed for nervous system disorders and mental disorders, but has also been applied to cancer patients (42-45). In one study, the authors explore if caregiver burden was in agreement with patient ratings. Patients had different forms of advanced cancer and their carer's Zarit scores were relatively low. They conclude that Zarit may not capture some important aspects of burden in cancer, given that it was initially developed for dementia patients (42). A second study used the ZBI to assess the impact of breathlessness in lung cancer patients on their caregivers, and found high levels of unmet needs and burden particularly in the more severe cases (43).

Assessment timing of the ZBI will be at the end of the study, and will be administered in paper format. Its criterion validity, construct validity and internal consistency have been demonstrated (40). The Italian version of the questionnaire is valid, reliable and useful for use in clinical contexts and in future studies (46).

(4) Usability and satisfaction of LuCApp

At the end of the study, patients in the intervention arm will have an opportunity to provide feedback on strengths and shortcomings of the application, including unintended/unexpected effects. This session will be of interest also for those who did not use the application as intended by the developers. Use and adoption metrics are important process outcomes to understand the mechanism of action of such intervention. The mHealth application contains a tracking system. Frequency and duration of logins and the activity will be recorded and evaluated. To test user satisfaction with the App, a modified computer system usability questionnaire (CSUQ) will be utilized at the end of the study and will be administered to both patients and clinicians using LuCApp. The CSUQ is an overall satisfaction questionnaire that was developed together with other subjective usability measures at IBM in the nineties (47). The CSUQ is identical to the Post-Study System Usability Questionnaire (PSSUQ),

[figure not shown]

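### The app is the only stated route for the LuCApp arm's patient questionnaires, including the week-12 FACT-L, while controls have three routes; LuCApp patients who stop using the app are at greater risk of a missing primary outcome.

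*Combined protocol and SAP*

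**What the plan says.** Under Participants, the plan sets the route by arm: "data will be collected through questionnaires via the app for the intervention patients, while standard-of-care patients will complete paper questionnaires during clinic visits". The same sentence gives controls two further options: "or at home (having received paper questionnaires during the previous visit) or via telephonic interviews with the research team". The Standard of care section repeats all three control routes. In Intervention (LuCApp), the questionnaire component of the app holds the EQ-5D, FACT-L, HADS and supportive care needs survey, and paper is mentioned for controls only. The Sample size section repeats the split for the primary instrument: "The FACT-L questionnaire will be administered electronically (via LuCApp) or via paper in the control group at baseline, 12 weeks and 24 weeks".

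Staff support follows the same pattern. Of the clinical teams looking after controls, the plan says "they will administer questionnaires when due and will update the CRF for the standard of care patients"; there is no matching statement for LuCApp patients. The explicit list of automated prompts reads "Participants will be prompted, via an automated message to update their body temperature and their weight and to fill out the side effects questionnaires" and does not name the FACT-L, although a more general sentence promises banners on days when scheduled entries are due.

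The primary outcome is the change in TOI from baseline to 12 weeks. Statistical methods compares it with a two-group t-test on change scores. Imputation appears as a set of sensitivity analyses.

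**The concern.** In the LuCApp arm the experimental product is also the measuring channel. A patient may be too unwell to use the app, may have lost or changed the phone, or may have given up on it. A site following the text has no stated way to obtain that patient's week-12 FACT-L. For a comparable control, the site can hand over a form in clinic, send one home or telephone.

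The primary t-test needs an observed week-12 score. If patients who disengage are doing worse than those who continue, the LuCApp mean is taken over a more favourable subset than the control mean, and part of any observed difference reflects who was measured. Week-12 scores that were not collected cannot be obtained later.

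The planned sensitivity analyses help only in part. The FACT-L is given at baseline, 12 and 24 weeks, so carrying the last observation forward to week 12 carries the baseline score. That sets the change to zero and hides any decline. No scenario is specified by arm or for stopping the app.

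**Working it through.** **Is there a fallback anywhere?** Each text that might supply one:

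- The technology-failure text in Intervention (LuCApp) concerns urgent clinical care, not outcome data.
- The weekend advice there and in Standard of care also concerns care.
- The helpdesk, in-app notifications and reminders support use of the app; they do not replace it.
- The description of the FACT-L allows several modes in general: "The administration mode could be interviews (in-person or telephone), self-administration (in the clinic or by mail) or computer administered questionnaire". It does not say that LuCApp patients will be offered them.

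So no alternative route is stated, and none is forbidden.

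**The plan's own figure.** Inputs from Sample size: difference 6, SD 11.54, two-sided 0.05, power 80%.

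n per arm = 2 × (1.960 + 0.842)² × 11.54² / 6² = 58.1, so 59 by the normal approximation. The t-test solution is 59.05, so 60 per arm, or 120 in total. The stated 120 evaluable patients is reproduced.

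**Upper-end illustration.** Assumptions, none given in the documents: a share p of LuCApp patients have no week-12 score because they stopped using the app; their TOI change is d points worse than that of the other LuCApp patients; all comparable controls are recovered.

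- The full-arm mean is p × d below the completers' mean, so bias = p × d.
- SE = 11.54 × √(2/60) = 2.107, keeping the plan's 60 per arm.
- Rejection rate with no true effect = Φ(−1.96 + bias/SE) + Φ(−1.96 − bias/SE).

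| p | d | Bias (points) | Share of 6 points | Type I error |
|---|---|---|---|---|
| 15% | 6 | 0.9 | 15% | 7.1% |
| 20% | 8 | 1.6 | 27% | 11.8% |
| 25% | 10 | 2.5 | 42% | 22.0% |

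If half of these LuCApp patients still completed the one week-12 form, the outer biases would halve to 0.45 and 1.25 points, with error rates of about 5.5% and 9.1%.

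**With losses in both arms.** Take 156 enrolled (78 per arm) and the plan's 30% attrition overall. The split by arm is assumed, and D is the deficit of non-completers in either arm. Bias = (missing in LuCApp − missing in control) × D, and SE = 11.54 × √(1/n₁ + 1/n₂).

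| Missing, LuCApp vs control | Completers | SE | Bias, D = 5 to 15 | Type I error |
|---|---|---|---|---|
| 35% vs 25% | 50.7 vs 58.5 | 2.21 | 0.5 to 1.5 | 5.6% to 10.4% |
| 40% vs 20% | 46.8 vs 62.4 | 2.23 | 1.0 to 3.0 | 7.3% to 27% |
| 45% vs 15% | 42.9 vs 66.3 | 2.26 | 1.5 to 4.5 | 10% to 51% |

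With equal missingness the bias term is zero. Power for a true 6-point difference hardly moves with the split (77.5% at 30/30, 75.6% at 45/15), so the issue is bias rather than precision.

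**The case against.** The strongest reply is that silence is not prohibition. The trial is described as not purely web-based, LuCApp patients are still seen in clinic, and the FACT-L can be given in several modes. A sensible site might simply hand over a paper form. That is true, but the text assigns routes by arm in several places, and two sites could reasonably act differently.

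Second, stopping daily use is not the same as losing the FACT-L, which needs a single completion at week 12. Banners and the helpdesk may bring many patients back for it. This stands, and it reduces the size.

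Third, the plan's remark about non-users, "This session will be of interest also for those who did not use the application as intended by the developers", concerns an end-of-study feedback session. It shows that imperfect use is foreseen; it does not forecast missing FACT-L forms.

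Fourth, the direction is not established. Patients may stop because they are unwell, or because they have few symptoms and little reason to log in. The study-participation rule in Randomization also removes patients from both arms when cancer treatment is discontinued, which narrows the group this mechanism can affect.

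Fifth, Statistical methods plans to assess whether data are missing at random, and includes multiple imputation and mixed models. These are sensitivity or secondary analyses and are not arm-specific, so they mitigate rather than remove the problem.

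Finally, the trial is labelled a feasibility study and pilot. It is nevertheless sized for a two-sided 5% test with 80% power, so bias in that comparison matters.

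**Conclusion.** The asymmetry is in the text and reaches the primary outcome: one stated route in the LuCApp arm, three in the control arm. It creates a differential risk of a missing week-12 score that could bias the comparison, plausibly towards LuCApp if those who disengage are sicker.

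The documents do not support several stronger readings that a reader might infer:

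- That all LuCApp outcomes depend on the app. Caregiver burden is collected on paper, and resource use has a physician-administered form in both arms.
- That equally ill controls would never be lost. Controls can also miss forms, and no procedure for pursuing them is described.
- That everyone who stops using the app loses the primary outcome, or that the bias certainly favours LuCApp.

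The 0.9–2.5 points (type I error about 7–22%) rest on assumed p and d, complete loss in one arm and complete recovery in the other, so they mark the upper end for those values of p and d. This should be fixed, on the grounds that prevention is cheap and lost scores cannot be recovered.

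**What to change.** Amend Participants, Intervention (LuCApp, questionnaire component), Standard of care and Sample size so that they say the same thing:

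1. If a LuCApp patient's FACT-L, EQ-5D-5L, HADS or SCNS-SF34 has not arrived through the app by a fixed day after its due date (the sponsor to set the day), the patient is offered clinic paper, home paper or a telephone interview, on the same terms as controls.
2. Stopping use of the app does not end outcome collection.
3. The route used is recorded for every questionnaire, and missingness is reported by arm.

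The cost is a wording change and a supply of existing forms to LuCApp patients; the visits and research team are already in place. The downside is some mixed-mode data in the LuCApp arm. The plan's own FACT-L section regards differences between modes as small and the formats as interchangeable for group-level reporting, so this is minor beside a missing score.
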